### **9.2.2.1 Analysis**

Pairwise comparison as Cochran Mantel Haenszel test adjusted by surgical procedure will be applied to the proportion.

## **9.2.3 Proportion of Patients with Nausea on Days 1 through 3**

Nausea will be as reported as an adverse event. The following proportions will be calculated by treatment group.

- (1) The proportion of patients who completed the study on Day 1, 2 and 3 with nausea between Day 1 and Day 3
- (2) The proportion of patients with nausea between first dosing and Day 1

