8.3 Adverse Events and Serious Adverse Events

The definitions of an AE and an SAE can be found in [Appendix 3](#).

Adverse events reported by the patient (or, when applicable, by a caregiver, surrogate, or the patient's legally authorized representative) must be captured in source documents. Abnormal laboratory test results, blood pressure, pulse rate, and ECG findings after the first dose that are considered to demonstrate a clinically significant change from baseline will be recorded in the eCRF as treatment-emergent adverse events (TEAEs).

The investigator and any qualified designees are responsible for detecting, documenting, and recording events that meet the definition of an AE or SAE and remain responsible for following up AEs that are serious, considered related to the study treatment or study procedures, or caused the patient to discontinue study treatment or withdraw from the study (see [Section 7](#)).

8.3.1 Time Period and Frequency for Collecting Adverse Event and Serious Adverse Event Information

All AEs/SAEs will be collected from the date of signing of the ICF until the End-of-study Visit at the time points specified in the SoA ([Section 1.3](#)).

All SAEs will be recorded in the eCRF and reported to the CRO within 24 hours of awareness, as indicated in [Appendix 3](#). The investigator or qualified designee will submit any updated SAE information to the CRO within 24 hours of awareness.

The investigators or qualified designees are not obligated to actively seek AEs or SAEs after conclusion of the study participation. However, if the investigator or qualified designee learns of any SAE, including a death, at any time after a patient is no longer in the study, and the investigator or qualified designee considers the event to be reasonably

related to the study treatment or study participation, the investigator or qualified designee must promptly notify the CRO via phone, e-mail, or fax (see [Appendix 3](#)). Investigator assessment of causality must be included with all SAEs reported to the CRO. Serious adverse events with missing investigator causality will be followed up urgently until provided to the CRO.

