8.3.2 Method of Detecting Adverse Events and Serious Adverse Events

The method of recording, evaluating, and assessing causality of AEs and SAEs and the procedures for completing and transmitting SAE reports are provided in [Appendix 3](#).

Care will be taken not to introduce bias when detecting AEs and/or SAEs. Open-ended and non-leading questioning of the patient is the preferred method to identify AEs.

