9.4.5.2 Secondary Efficacy Endpoints

Secondary efficacy endpoints will be as follows:

- Time from the end of surgery (as defined for the primary endpoint) to time when the discharge order is written
- Proportion of patients requiring postoperative reinsertion of the nasogastric tube
- Proportion of patients with nausea on Days 1 through 3
- Proportion of patients with vomiting on Days 1 through 3
- Proportion of patients discharged by Day 10 who are readmitted for any reason within 30 days after discharge from the hospital

For time from the end of surgery to time when the discharge order is written, the same KM approach as used for the primary efficacy analysis will be performed. The proportion of patients for each of the other parameters will be summarized by treatment group.

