
• Any abnormal laboratory test results (hematology or clinical chemistry) or other safety assessments (eg, ECG, radiological scans, vital signs measurements), including those that worsen from baseline, considered clinically significant in the medical and scientific judgment of the investigator (ie, not related to progression of underlying disease).• Exacerbation of a chronic or intermittent preexisting condition including an increase in frequency and/or intensity of the condition.• New conditions detected or diagnosed after study treatment administration even though they may have been present before the start of the study.• Signs, symptoms, or the clinical sequelae of a suspected drug-drug interaction.• Signs, symptoms, or the clinical sequelae of a suspected overdose of either study treatment or a concomitant medication. Overdose per se will not be reported as an AE/SAE unless it is an intentional overdose taken with possible suicidal/self-harming intent. Such overdoses should be reported regardless of sequelae.• “Lack of efficacy” or “failure of expected pharmacological action” per se will not be reported as an AE or SAE (unless fatal). Such instances will be captured in the efficacy assessments. However, the signs, symptoms, and/or clinical sequelae resulting from lack of efficacy will be reported as an AE or SAE if they fulfil the definition of an AE or SAE.• The signs, symptoms, and/or clinical sequelae resulting from lack of efficacy will be reported as an AE or SAE if they fulfil the definition of an AE or SAE.

Events NOT Meeting the AE Definition

- Any abnormal laboratory findings or other abnormal safety assessments which are associated with the underlying disease, unless judged by the investigator to be more severe than expected for the patient's condition.
- The disease/disorder being studied or expected progression, signs, or symptoms of the disease/disorder being studied, unless more severe than expected for the patient's condition.
- An elective procedure not reflecting a worsening of a known underlying medical condition is not considered an AE, and therefore will not be considered an SAE despite requiring hospitalization. However, complications of a procedure will be considered an AE and may be considered an SAE if hospitalization is prolonged (or any other SAE criterion is met).

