10.3.2 Recording and Follow-up of Adverse Events and Serious Adverse Events

AE and SAE Recording

- When an AE/SAE occurs, it is the responsibility of the investigator to review all documentation (eg, hospital progress notes, laboratory reports, and diagnostics reports) related to the event.
- The investigator will then record all relevant AE/SAE information in the eCRF.
- It is **not** acceptable for the investigator to send photocopies of the patient's medical records/discharge summary to the CRO in lieu of completion of the AE/SAE CRF page.
- There may be instances when copies of medical records for certain cases are requested by the CRO. In this case, all patient identifiers, with the exception of the patient number, will be redacted on the copies of the medical records before submission to the CRO.
- The investigator will attempt to establish a diagnosis of the event based on signs, symptoms, and/or other clinical information. Whenever possible, the diagnosis (not the individual signs/symptoms) will be documented as the AE/SAE.

Assessment of Intensity

The investigator will make an assessment of intensity for each AE and SAE reported during the study and assign it to 1 of the following Common Terminology Criteria for Adverse Events (CTCAE) Version 5.0 grades

(https://ctep.cancer.gov/protocolDevelopment/electronic_applications/ctc.htm#ctc_50):

- Grade 1 Mild; asymptomatic or mild symptoms; clinical or diagnostic observations only; intervention not indicated.
- Grade 2 Moderate; minimal, local or noninvasive intervention indicated; limiting age-appropriate instrumental activities of daily living (ADL)*.
- Grade 3 Severe or medically significant but not immediately life-threatening; hospitalization or prolongation of hospitalization indicated; disabling; limiting self care ADL**.
- Grade 4 Life-threatening consequences; urgent intervention indicated.
- Grade 5 Death related to AE.
 - * Instrumental ADL refer to preparing meals, shopping for groceries or clothes, using the telephone, managing money, etc.
 - ** Self care ADL refer to bathing, dressing and undressing, feeding self, using the toilet, taking medications, and not bedridden.
- An event is defined as serious when it meets at least 1 of the predefined outcomes as described in the definition of an SAE, NOT when it is rated as Grades 3, 4, or 5.
- The highest severity during the period in which the AE occurred will be recorded in the eCRF.

Assessment of Causality

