## **9.2.4 Proportion of Patients with Vomiting on Days 1 through 3**

Vomiting will be as reported as an adverse event. The proportions described in section 9.2.3 will be calculated for vomiting.

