### **9.3.5 Proportion of Patients with Abdominal Distension on Day 1 through the Day on which GI2 is Achieved**

Abdominal distension will be as reported as an adverse event. The following proportions in the mITT Population will be calculated.

- (1) The proportion of patients who achieved GI2 after Day 1
  - a) And who had abdominal distension on Day 1 through the day on which GI2 is achieved
  - b) And who had abdominal distension other than the time window above in a) from first dose to Day 10 or withdrawal or discharge day.
  - c) And who did not have abdominal distension
- (2) The proportion of patients who did not achieve GI2 after Day 1
  - a) And who had abdominal distension from first dose to Day 10 or withdrawal or discharge day
  - b) And who did not have abdominal distension

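### The nausea, vomiting and abdominal distension endpoints rest on AE reports alone, under AE rules that sites can reasonably read as leaving such symptoms out, so events can be under-counted and captured unevenly across sites

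*SAP*

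**What the plan says.** The protocol lists the endpoint without naming a data source: "Proportion of patients with nausea on Days 1 through 3" (Protocol 9.4.5.2), with a matching item for vomiting. Protocol 9.4.5.3 adds, as exploratory endpoints, nausea and vomiting from Day 4 to discharge, and abdominal distension from Day 1 to the day GI2 is achieved.

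The SAP supplies the source:

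- SAP 9.2.3 (and again in 9.3.6): "Nausea will be as reported as an adverse event".
- SAP 9.2.4 (and again in 9.3.7): "Vomiting will be as reported as an adverse event".
- SAP 9.3.5: "Abdominal distension will be as reported as an adverse event".

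The protocol then governs what reaches the AE form:

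- Period (8.3.1): "All AEs/SAEs will be collected from the date of signing of the ICF until the End-of-study Visit".
- Detection (8.3.2): "Open-ended and non-leading questioning of the patient is the preferred method to identify AEs".
- Not an AE (Appendix 3, list of events not meeting the definition): "The disease/disorder being studied or expected progression, signs, or symptoms of the disease/disorder being studied, unless more severe than expected" for the patient's condition.
- Recording (10.3.2): "Whenever possible, the diagnosis (not the individual signs/symptoms) will be documented as the AE/SAE".

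**The concern.** An efficacy endpoint needs the same question put to every patient on every day of its window. AE collection serves another purpose: it looks for untoward events, leaves the prompting open and filters what is entered. Here the filter touches the symptoms being counted. The study rationale (Protocol 2.1) is postoperative GI dysfunction, and nausea, vomiting and distension are plausible expected symptoms of it. A site that regards a patient's nausea as expected may enter nothing. A site that diagnoses ileus may enter ileus alone. Either way the patient is analysed as having had no nausea.

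At stake are the pairwise Cochran-Mantel-Haenszel comparisons in SAP 9.2.3.1, 9.2.4.1, 9.3.5.1, 9.3.6.1 and 9.3.7.1. Missed events pull the proportions down. Equal loss in both arms shrinks the risk difference, and unequal loss can distort it. Sites that draw the line at expected in different places add variation unrelated to treatment. The primary GI2 analysis is not affected.

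**Working it through.** **1. Is there another source?** The efficacy rows of the Schedule of Activities (Protocol Figure 1-2) cover nasogastric tube re-insertion, GI2, discharge readiness, discharge order, actual discharge and readmission. None covers nausea, vomiting or distension. Protocol 8.1.2 and 8.1.3 have no assessment section for these five endpoints. Three related observations exist, but none is used to derive them:

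- The GI item of the COWS (Appendix 9) looks back half an hour and scores nausea together with loose stool.
- Vomiting within 1 hour of dosing (Protocol 6.4) is compliance data.
- The judgement of significant nausea or vomiting in the 4 hours after solid food (Protocol 8.1.1.1) serves GI2.

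**2. Which way do the AE rules push?** The exclusion of expected symptoms and the preference for a diagnosis can each remove a symptom entry; neither can add one. The possible counterweight is the Appendix 3 text on lack of efficacy, which calls for resulting symptoms to be reported. It does so only where they fulfil the AE definition, which leads back to the exclusion. The instruction is therefore ambiguous, and the likely direction of error is downward.

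**3. Is there a figure to reproduce?** No. The documents give no event rate, effect size or power for these endpoints. The 44 to 85 per group in Protocol 9.2 and SAP 4.2 is sized for the linear trend in GI2 restricted mean survival time.

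**4. Illustration (every rate and capture share is assumed).** Let p0 and p1 be the true proportions and s the share of true cases that reach the AE form. If s is the same in both arms:

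observed difference = s·p0 − s·p1 = s·(p0 − p1)

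With a = s·p0, b = s·p1, m = (a + b)/2 and a two-sided 0.05 test (SAP 6.2), unstratified:

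power ≈ Φ{ [ |a − b|·√n − 1.96·√(2m(1 − m)) ] / √( a(1 − a) + b(1 − b) ) }

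Example: p0 = 0.50, p1 = 0.30, n = 50, s = 0.6. Then a = 0.30, b = 0.18 and m = 0.24. The numerator is 0.12 × 7.071 − 1.96 × 0.604 = 0.849 − 1.184 = −0.335, the denominator is 0.598, and Φ(−0.56) = 0.29.

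Power for assumed true rates of 50% and 30%:

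| n per group | s = 1.0 | s = 0.8 | s = 0.6 | s = 0.4 |
|---|---|---|---|---|
| 44 | 48% | 36% | 26% | 17% |
| 50 | 53% | 40% | 29% | 19% |
| 85 | 76% | 61% | 45% | 29% |

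Other assumed pairs behave alike. Across 60/40, 50/30 and 30/15 at 50 per group, power is 43% to 53% at s = 1.0 and 26% to 29% at s = 0.6. For 40/20 at 85 per group it runs 82%, 69%, 53% and 36% across the four shares.

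**5. Unequal capture (assumed).** With capture of 0.6 on placebo and 0.8 on active, and true rates of 50% and 30%, the observed rates are 0.6 × 50% = 30% and 0.8 × 30% = 24%. A 20-point difference shows as 6 points, and power is 10% at 50 per group and 14% at 85. Nothing in the documents indicates whether capture would differ by arm, or in which direction.

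**The case against.** The case for leaving the plan alone has substance.

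- A reader might infer that the endpoints rest on spontaneous reports. They do not. Investigators are responsible for detecting events (Protocol 8.3), patients are questioned, and AE assessment runs continuously through the Schedule of Activities. What is missing is a structured symptom question.
- A reader might infer that sites are told not to report nausea, vomiting or distension. No passage says these symptoms fall under the exclusion. The general AE definition in Appendix 3 takes in any unfavourable and unintended symptom, the diagnosis rule applies only whenever possible, and SAP 10.1 with Table 4 plans a plot of gastrointestinal preferred terms, so the plan evidently expects such AEs. The result is ambiguity, not a ban.
- A reader might infer that events are certain to be under-counted, or that only severe cases will be captured. The documents support only that this can happen. COWS and the GI2 food assessment prompt staff to notice these symptoms, which makes very low capture less plausible.
- The power figures have no anchor in the documents, ignore the stratification, and mostly assume equal capture. Even with complete capture, 50 per group gives only 53% in the example, so these comparisons are weak in any case.
- These are secondary and exploratory endpoints in a Phase 2 study without multiplicity control, and Protocol 9.4.5.2 promises only summaries for the proportions.

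All of this limits the claim and its priority. It does not close the gap: SAP sourcing and the Appendix 3 rules are not reconciled, and no other record feeds the endpoints.

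**Conclusion.** The point holds as a risk to data capture. Five endpoints are taken only from AE reports, without a scheduled symptom assessment, under two recording rules that sites can reasonably apply to the very symptoms being counted. Events can be under-counted and inconsistently captured across sites. That these symptoms count as expected features of postoperative GI dysfunction is a reasonable inference, not something the documents state.

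The loss cannot be sized. Equal capture s shrinks the risk difference to s times its true value, and that relation is the only firm quantity. The power figures are illustrative. Differential loss by arm is possible but not shown. This is a cheap improvement worth making, not a threat to the primary conclusion.

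**What to change.** Preferred: add daily yes/no eCRF items for nausea, vomiting and abdominal distension, and derive SAP 9.2.3, 9.2.4 and 9.3.5 to 9.3.7 from them instead of from AE reports.

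- Window: Day 1 to discharge for nausea and vomiting; Day 1 to the day of GI2 for distension. Where GI2 falls after discharge, the distension question can join the daily contact that Protocol 8.1.1.1 already specifies up to Day 10.
- Recall: ask by calendar day, since SAP 6.5.1 starts each study day at midnight. A morning question on the past 24 hours, as in the NPRS, would bring part of Day 0 into Day 1.
- The descriptive companion proportions that use other windows (SAP 9.2.3 item 2; 9.3.5 items 1b and 2a) start at first dose. Either extend the items to cover them or label those rows as AE-based.

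Minimum: state in Appendix 3 that these three symptoms are always recorded individually over those windows, whether or not expected and whether or not part of a diagnosis.

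Cost: a short amendment, three eCRF items and slight daily site burden. The minimum option also raises TEAE counts in the safety tables, which should be said when they are presented. It leaves detection to open-ended questioning, so the preferred option is better.

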4.4 End of Study Definition

The end of the study is defined as the date of the last visit of the last patient in the study. A patient is considered to have completed the study if he/she has completed all periods of the study through the End-of-study Visit, even if he or she completes study treatment prior to Day 10 because of meeting the primary endpoint, GI2 (see SoA in Section 1.3).

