9.4.5 Efficacy Analyses

The mITT Population will be the primary population for efficacy analyses.

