## 9. EFFICACY

Efficacy analyses will be performed for the mITT population unless otherwise specified.

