### **9.2.3.1 Analysis**

Pairwise comparison as Cochran Mantel Haenszel test adjusted by surgical procedure will be applied to the proportion of patients who completed the study on Day 1, 2 and 3 with nausea between Day 1 and Day 3 defined in 1) of section 9.2.3.

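### The tested Days 1–3 nausea and vomiting endpoints are limited to an undefined group of patients who completed those days, a restriction the protocol does not contain and the SAP does not justify

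*SAP*

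**What the plan says.** Protocol 9.4.5.2 lists the secondary endpoint as "Proportion of patients with nausea on Days 1 through 3", with a matching line for vomiting. Neither line carries a completion condition. Protocol 9.4.5 sets the general rule: "The mITT Population will be the primary population for efficacy analyses". SAP Section 9 repeats it with room for exceptions: "Efficacy analyses will be performed for the mITT population unless otherwise specified".

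SAP 9.2.3 takes nausea from adverse event reports and defines two proportions. Item (1) is "The proportion of patients who completed the study on Day 1, 2 and 3 with nausea between Day 1 and Day 3". Item (2) is "The proportion of patients with nausea between first dosing and Day 1". Only item (1) is tested: under SAP 9.2.3.1 the Cochran-Mantel-Haenszel comparison is "applied to the proportion of patients who completed the study on Day 1, 2 and 3 with nausea". SAP 9.2.4 says "The proportions described in section 9.2.3 will be calculated for vomiting", and 9.2.4.1 uses the same analysis.

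The SAP does not say what completing the study on these days means. The protocol's only definition, in Section 4.4, is of a different kind: "A patient is considered to have completed the study if he/she has completed all periods of the study through the End-of-study Visit". Protocol 9.4 requires changes from the protocol's analyses to be set out and justified in the SAP. The SAP gives no justification for this one.

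**The concern.** Whether a patient completes Days 1 to 3 is known only after randomisation and may depend on the symptoms being measured. Conditioning on it gives up the randomised comparison for these endpoints.

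It also discards data already in hand. Protocol 8.3.1 collects adverse events from consent to the End-of-study Visit, so an event on Day 1 or Day 2 is on record even if the patient then withdraws. The rule against imputation in SAP 6.4 does not explain leaving it out, since nothing is missing.

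Because the term is undefined, two programmers could produce different tested results from the same data.

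**Working it through.** The documents state no nausea rate, no early-withdrawal rate and no power for these endpoints, so there is no figure of the plan's to reproduce. The check compares the definitions and then illustrates their effect with assumed counts.

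**1. The definitions side by side.** The table assumes that each patient meets the protocol's definition of the mITT (at least one dose and at least one post-baseline assessment for the primary endpoint).

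| Patient | Protocol endpoint | Tested proportion, SAP 9.2.3(1) |
|---|---|---|
| Nausea on Day 1, leaves the study on Day 2 | Event | Not an event |
| No nausea, leaves the study on Day 2 | In the mITT; scoring not stated | Excluded, or a non-event if the condition applies only to the numerator |
| No nausea, discharged on Day 2, still in the study | Non-event | Non-event or excluded, depending on what completing means |
| Nausea on Day 1, discharged on Day 2, still in the study | Event | Event or not, depending on what completing means |

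The last two rows are open because SAP 9.3.6, the parallel endpoint from Day 4, lists discharge before Day 4 as a category separate from completing up to at least Day 4. By analogy, a patient discharged before the end of Day 3 might be treated as not completing.

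**2. If symptomatic patients leave.** Assume 50 patients in a group, 20 with nausea on Days 1–3, and 5 of those 20 leaving before the end of Day 3.
- All patients, all recorded events: 20/50 = 40.0%.
- Condition applied to the denominator: (20 − 5)/(50 − 5) = 15/45 = 33.3%.
- Condition applied to the numerator only: 15/50 = 30.0%.

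The rate falls on either reading.

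**3. If early discharge counts as not completing.** Assume again 20 of 50 with nausea, and that 25% of the 30 patients without nausea are removed because they went home early. The estimate is 20/(20 + 0.75 × 30) = 20/42.5 = 47.1%. The rate rises.

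**4. Effect on a comparison.** Assume 50 per arm (the lower planned number in the Protocol 1.1 synopsis), equal true rates of 20/50 = 40.0%, and 3 leavers in each arm, all ill in arm A and none ill in arm B.
- Condition on the denominator: A = 17/47 = 36.2%, B = 20/47 = 42.6%. The difference is 3/47 = 6.4 points, where the true difference is 0. With equal true rates this holds whatever the common rate.
- Condition on the numerator only: A = 17/50 = 34.0%, B = 20/50 = 40.0%. The difference is 6.0 points.
- All 50 patients as denominator, all recorded events counted: 20/50 against 20/50, difference 0.
- If the 3 leavers were ill in both arms, both would show 17/47 and the difference would not move.

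The count of 3 and the complete split by symptoms are assumptions, and the split is an extreme one.

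**5. Would replacing completers by the mITT be enough?** SAP 5.1 adds to the protocol's mITT definition that the post-baseline assessment includes all three components of GI2: end of surgery, toleration of solid food and first bowel movement. If that means all three must be observed, a patient who leaves before GI2 is already outside the SAP's mITT. Changing only 9.2.3 and 9.2.4 would then not bring that patient back.

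**The case against.** **Other outputs count these patients.** Item (2) of SAP 9.2.3 has no completion condition and, if Day 1 is included, would count a patient with nausea on Day 1 who then withdraws. The adverse event tables also report nausea and vomiting in the Safety Analysis Population, withdrawals included. Both points are correct, but neither repairs the tested comparison. Item (2) covers a different window and is not tested, and the adverse event tables are not restricted to Days 1–3.

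**The SAP allows exceptions to the mITT.** It does, and 9.2.3 may be one. That permits a different population but does not supply the justification that Protocol 9.4 requires. A reader might infer that the protocol defines this endpoint on the mITT. That is too strong: the endpoint line names no denominator, and the mITT comes from the general rule in Protocol 9.4.5.

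**Few patients may be affected.** Protocol 7.2 asks patients who stop treatment to remain in the study to the End-of-study Visit unless there is a safety reason, so true exits by Day 3 may be rare. This stands, and it limits the likely size.

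**The exit rate might be taken from the sample-size section.** Protocol 9.2 assumes about 20% exponential censoring by 240 hours, and 1 − 0.8^(72/240) = 6.5% by 72 hours. A reader might use this as the share that has left by Day 3. The documents do not support that. It is a simulation assumption about censoring of GI2 time, not a forecast of study exit, and it takes censoring to be independent, whereas the worry here is exit linked to symptoms.

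**Conclusion.** The point holds as a defect of definition. The SAP tests nausea and vomiting on Days 1–3 in an undefined post-randomisation subset, without the justification the protocol calls for, and recorded events in patients who leave the study early do not count.

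A reader might infer that the restriction necessarily lowers the rates and so flatters the less well tolerated dose. The documents do not fix the direction. Rates fall if symptomatic patients withdraw, and rise if patients discharged early, probably the faster recoverers, are dropped.

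The size cannot be established from the documents. The 6.0 to 6.4 points above rest on assumed exits of 3 of 50 in each arm, equal true rates and an extreme split by symptoms; balanced exits would give less.

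Importance is modest. These are secondary endpoints of a Phase 2 trial without multiplicity adjustment, and they did not drive the sample size. The correction is cheap and worth making before unblinding.

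**What to change.** In SAP 9.2.3 and 9.2.4:
- Use all mITT patients, as the protocol defines the mITT, as the denominator for the Cochran-Mantel-Haenszel test.
- Count as an event any nausea (or vomiting) adverse event from Day 1 to the earlier of the end of Day 3 or leaving the study.
- Keep patients discharged before Day 3 in the denominator.
- State that patients who leave the study by then without an event count as non-events, and add a sensitivity analysis that excludes them.
- Define completion of Days 1 to 3, and keep the completer version as a supplementary table.

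In SAP 5.1, reconcile the mITT with the protocol so that membership does not require all three GI2 components to be observed. Without this, the new denominator could still leave out early leavers.

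The cost is SAP text and the programming of these derivations; no new data are needed. The change to 5.1 reaches further, because every mITT analysis uses that definition. The small downside is that early leavers without symptoms are scored as non-events, which the sensitivity analysis makes visible.
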